The informed consent process will include a privacy authorization compliant with 45CFR164.508(c) via the inclusion/incorporation of:

- all core elements specified in 508(c)(1) including the signature of the individual (or representative) and date of signature,
- all required statements specified in 508(c)(2)
- the plain language requirement as specified in 508(c)(3), and
- the provision to the participant (or representative) a copy of the signed authorization (508(c)(4)

State of California Human Experimentation Requirements

This research involves the collection of information via validated questionnaires and obtaining information from the medical record. Research activities do not encompass those that are requisite for a participant to be involved in a “medical experiment” as defined by California State Law 24174. The ‘California Experimental Subject’s Bill of Rights’ will be administered as part of the informed consent process; as part of that process participants will receive a copy of the ‘Bill of Rights’ marked with their signature.

Data Management

Study data will be stored in secure password-protected servers. Study staff will de-identify all data prior to data analysis. Data will be analyzed to compare the safety and efficacy of Veillonella vs placebo and between the two different doses of Veillonella. We will also use these data to better understand the type of benefits different subsets of participants tend to experience as well as the magnitude of the benefit in these subpopulations. These results will be used to create peer-reviewed publications, academic and industry presentations, file patents, and potentially develop new innovative microbiome products like probiotics. Participants will not be notified of any of these uses.

Confidentiality

All documents and electronic data will be stored on secure, password-protected computers. Participant confidentiality will be strictly held in trust by the investigators, study personnel, and sponsor. No identifiers will be used in any subsequent publication of these results.

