The publication or presentation of any study results shall comply with all applicable privacy laws, including, but not limited to, the Health Insurance Portability and Accountability Act of 1996. Neither the complete nor any part of the results of the study carried out under this protocol, nor any of the information provided by the sponsor for the purposes of performing the study, will be published or passed on to any third party without the written approval of the Study PI. Any investigator involved with this study is obligated to provide the sponsor with all data derived from the study.

Biostatistical Analysis Plan

Data Source

The source of the data is the results of the questionnaires filled out through the Chloe app as well as the optional fitness tracker data collected over the course of the study.

Analysis Objectives

The goals of this analysis are to identify whether there are statistically significant differences in effects between the placebo and Veillonella groups as well as between the high and low dose Veillonella groups. Furthermore, for any differences that are observed, we would like to understand whether there are any demographic or other participant characteristics that may be associated with benefits or side effects experienced by the participants.

Analysis Sets / Populations / Subgroups

The three groups compared in this study are high dose Veillonella, low dose Veillonella, and placebo.

In addition, we plan to separately analyze results by gender, age, baseline exercise habits, health history, previous probiotic experience, sleep habits, and other lifestyle factors.

For those participants who share fitness tracker data, the fitness tracker data shared through the Chloe app will be analyzed in conjunction with survey data separately from those who did not share fitness tracker data.

Endpoints

The primary endpoints analyzed in this study are:

- Change in reported physical fatigue
- Change in mental / emotional fatigue
- Change in MFI

The secondary endpoints analyzed in this study are:

- Change in reported sleep quality
- Change in frequency of reported physical activity
- Change in intensity of reported physical activity
- Change in reported exercise
- Change in recovery time
- Change in energy level

The exploratory endpoints analyzed in this study are:

- Changes in fitness tracker data
- Change in reported bowel movements
- Change in GSE
- Change in reported mood
- Change in reported digestive health

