- Change in reported general health
- Change in BMI, weight, or waist circumference

Handling of Missing Values

There will likely be missing values related to incomplete or missing surveys. Participants will only be included in the analysis if they completed at least 50% of weekly surveys during each time period: baseline, supplementation, and washout. Values will be binned longitudinally such that each participant included in the analysis has a data point associated with each bin. If there are multiple values associated with a participant in a bin, the mean of those values will be used for the analysis.

Statistical Procedures

The majority of primary and secondary endpoints for this study are questions on the survey which consist of rating scales (generally 1-5 or 1-9). Significant differences between groups for these endpoints will be assessed using an independent T test or Mann-Whitney U test depending on the observed

distribution of the data. For significant changes over time within the same group, a dependent T test will be used.

For differences between groups in terms of primary and secondary endpoints that measure a change in time (e.g. time to recovery in days or hours of sleep), an independent T test or Mann-Whitney U test will be used, depending on the observed distribution of the data. For significant changes over time within the same group, a dependent T test will be used.

To identify demographics associated with any particular response (benefit or side effects), we will use the demographic, health history, and lifestyle information collected in the surveys to build an unsupervised machine learning algorithm (e.g. Random Forest Classifier). If we can build one that effectively classifies the response (AUC > 0.7), we will identify the model's most important features. To confirm that these features are significantly associated with response, we will use an independent T test to assess significant differences between response and non-response.

For all other exploratory endpoints including the optional fitness tracker data, the data type and distribution of that data will determine the statistical analysis used.

Measures to Adjust for Confounders

For all data and endpoints, data can be normalized to the baseline collected values, and change in value at different time points can be compared using the statistical tests described above.

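### Three unranked primary endpoints and two or three arm contrasts, with no alpha, testing order, adjustment or success rule: if any one result may count, the chance of a false primary result is about 16% to 32%

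*Combined protocol and SAP*

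**What the plan says.** Under Analysis Objectives, the Biostatistical Analysis Plan sets out to find "statistically significant differences in effects between the placebo and Veillonella groups as well as between the high and low dose Veillonella groups". The Endpoints section opens with "The primary endpoints analyzed in this study are" and lists three items without rank: change in physical fatigue, change in mental or emotional fatigue, and change in MFI. Statistical Procedures gives the test: "Significant differences between groups for these endpoints will be assessed using an independent T test or Mann-Whitney U test", with paired t tests for change within a group. No global test across the three arms comes first.

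The set of contrasts can be read in two ways:

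- Analysis Sets / Populations / Subgroups says "The three groups compared in this study are high dose Veillonella, low dose Veillonella, and placebo", which points to all three arm pairs.
- Data Management says "Data will be analyzed to compare the safety and efficacy of Veillonella vs placebo and between the two different doses of Veillonella", which can also mean pooled Veillonella v placebo plus high v low dose.

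Timing is partly open. Handling of Missing Values requires participants to have "completed at least 50% of weekly surveys during each time period: baseline, supplementation, and washout" and adds "Values will be binned longitudinally such that each participant included in the analysis has a data point associated with each bin". Measures to Adjust for Confounders says "change in value at different time points can be compared using the statistical tests described above". Table 2 fixes the MFI at the end of Weeks 2 and 6. Table 1 describes the MFI by five dimensions and mentions no total score.

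The documents state no alpha, sidedness, order among the primary endpoints or contrasts, adjustment, or definition of a positive study. The labels primary, secondary and exploratory rank tiers of endpoints only.

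**The concern.** With three primary endpoints and two or three contrasts, the plan yields six or nine primary tests and does not say how many must succeed, or which. Nothing prevents a single nominal p-value from being reported as a positive primary result, and a reader could not tell whether it was the planned one.

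This matters because the Background presents the study as a test of the benefit hypothesis and as confirmation of earlier effects in a broader population. Data Management and Intended Use of the Data foresee publications, patents and promotional material.

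Two looser definitions widen the choice. Supplementation period minus baseline period is the natural window for the weekly ratings, but it is not stated, and Details Study Procedures also wants to learn about lasting effects in washout. The MFI could be analysed as a total or by any of five dimensions.

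**Working it through.** The plan gives no error rate or power figure to reproduce, so the rates below are derived from its design.

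**Inputs from the documents.** Three primary endpoints (Endpoints); three arms allocated 4:4:2 to high dose, low dose and placebo (Details Study Procedures); pairwise two-sample tests (Statistical Procedures).

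**Assumptions, not in the documents.** Two-sided 0.05 per test; correlation between endpoints of 0, 0.5 or 0.9. All three endpoints are self-reported fatigue, so 0 is an upper bound on the error rate rather than a likely value.

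**Step 1: correlation between contrasts.** Under the null, arm means have variances proportional to 1/4, 1/4 and 1/2.

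- High v placebo and low v placebo share the placebo arm: correlation = (1/2) / (1/4 + 1/2) = 0.67.
- Pooled v placebo and high v low: covariance = (1/2)(1/4) − (1/2)(1/4) = 0, so they are independent.

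**Step 2: bound if all tests were independent.** 1 − 0.95^6 = 26.5%; 1 − 0.95^9 = 37.0%. The first is exact for pooled v placebo plus high v low when the endpoints are uncorrelated. The second is too high for three arm pairs because they share arms.

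**Step 3: simulation.** At least 1,000,000 null trials per setting, z tests on (difference in means) / sqrt(1/a_i + 1/a_j), with a = 4, 4, 2.

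| Chance of at least one false result | corr. 0 | corr. 0.5 | corr. 0.9 |
|---|---|---|---|
| Three arm pairs, nine tests, either direction | 32.1% | 28.3% | 19.4% |
| Pooled v placebo plus high v low, six tests, either direction | 26.5% | 23.6% | 16.0% |
| Each dose v placebo only, six tests, either direction | 23.4% | 20.6% | 13.9% |
| Pooled v placebo only, three tests, either direction | 14.3% | 12.5% | 8.4% |
| False benefit over placebo, two doses | 12.2% | 10.3% | 6.9% |
| False benefit over placebo, pooled | 7.3% | 6.3% | 4.2% |

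For one test, the chance of a false benefit is 0.05 / 2 = 2.5%.

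**Step 4: the same families under a stated rule.**

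| Rule | corr. 0 | corr. 0.5 | corr. 0.9 |
|---|---|---|---|
| All three endpoints significant in some contrast, three pairs | 0.04% | 0.9% | 5.8% |
| All three endpoints significant, pooled plus high v low | 0.03% | 0.6% | 4.5% |
| Holm, nine tests | 4.5% | 4.2% | 2.8% |
| Holm, pooled plus high v low (six tests) | 4.9% | 4.5% | 3.1% |
| Holm, each dose v placebo (six tests) | 4.5% | 4.1% | 2.8% |

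**Step 5: price in power.** Detectable difference in SD at 80% power = (z + 0.842) × sqrt(1/n1 + 1/n2). The z value is 1.960 at 0.05, 2.638 at 0.05/6 and 2.773 at 0.05/9; the last two are Holm's strictest step. Example, 400 v 200: sqrt(1/400 + 1/200) = 0.0866, so 2.802 × 0.0866 = 0.24 and 3.480 × 0.0866 = 0.30. The totals are illustrative: Recruitment gives 1,000 as an estimate of those invited, not analysed.

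| Total analysed | Dose v placebo: 0.05 | 0.05/6 | 0.05/9 | Pooled v placebo: 0.05 | 0.05/6 |
|---|---|---|---|---|---|
| 1,000 | 0.24 | 0.30 | 0.31 | 0.22 | 0.28 |
| 500 | 0.34 | 0.43 | 0.44 | 0.31 | 0.39 |
| 300 | 0.44 | 0.55 | 0.57 | 0.40 | 0.50 |

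**The case against.** The strongest reply is that the plan never says any one result suffices, so the inflated rates rest on a rule supplied by the reader. If all three endpoints had to succeed, the error would mostly stay below 5%. That is true, and it is why the rates are conditional. But the plan does not state the all-three rule either, and with three arm pairs and highly correlated endpoints even that rule reaches 5.8%.

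Second, the upper figures count harm as well as benefit, and they assume uncorrelated measures of what is largely the same thing; the MFI itself has physical and mental fatigue dimensions. This stands. The false-benefit rows and the 0.9 column are the more relevant figures for an efficacy claim, and they still exceed 2.5%.

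Third, no section calls high v low a primary contrast. Without it, the either-direction rates fall to 14% to 23% (each dose v placebo) or 8% to 14% (pooled). This also stands, but Analysis Objectives gives that contrast equal standing with the placebo comparison, so counting it follows the text.

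Finally, this is a minimal-risk supplement study with one descriptive objective. That would excuse looser control if every endpoint were exploratory. The plan instead separates primary from exploratory endpoints and says it tests a hypothesis.

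**Conclusion.** The concern holds. The documents define no alpha, order, adjustment or success rule for six to nine primary tests, and they leave the contrasts open. If any one nominal result may count, at an assumed 0.05 two-sided per test and endpoint correlation of 0.9 to 0, the familywise error is 16% to 32% across the two readings that include high v low. The narrower risk of a false benefit over placebo is 4% to 12%. The unfixed window and MFI score can only add to these rates; no figure is claimed for that. The gap must be closed before arms are compared, because a rule chosen afterwards cannot be credited as prespecified.

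**What to change.** Before any outcome is compared by arm, amend the SAP to:

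1. State two-sided alpha 0.05 for the primary family.
2. Name the contrasts in that family: each dose v placebo, or pooled Veillonella v placebo. If high v low remains a primary goal, include it or place it later in the sequence; otherwise label it secondary.
3. Name one MFI score, and one window for the weekly ratings, for example supplementation-period mean minus baseline-period mean.
4. Control familywise error across the family by Holm or by a fixed sequence.
5. Base efficacy claims on the between-group tests and report within-arm changes descriptively. A paired test in one arm cannot separate a product effect from placebo response or change over time.

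This needs SAP wording only and no new data. The price of Holm is power: with 1,000 analysed and six dose-v-placebo tests, its strictest step raises the detectable difference by about 0.06 SD, and by about 0.11 SD with 300. A fixed sequence leaves the first test at full alpha, but no later test can be claimed once one fails, so the order must be chosen with care.

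### Subgroup results are to be analysed level by level with no test of interaction, so chance differences in significance could be read as differential benefit

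*Combined protocol and SAP*

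**What the plan says.** Analysis Sets / Populations / Subgroups names the three arms and then states: "we plan to separately analyze results by gender, age, baseline exercise habits, health history, previous probiotic experience, sleep habits, and other lifestyle factors". That is six named factors and an open-ended remainder. No levels or cut-points are given.

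Two other places show what the results are for. Data Management wants to understand "the type of benefits different subsets of participants tend to experience as well as the magnitude of the benefit in these subpopulations". Analysis Objectives asks, where differences have been seen, "whether there are any demographic or other participant characteristics that may be associated with benefits or side effects experienced by the participants".

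Statistical Procedures names the tests. Between groups it is "an independent T test or Mann-Whitney U test depending on the observed" distribution of the data. Within a group: "For significant changes over time within the same group, a dependent T test will be used". Neither the plan nor the protocol mentions an interaction or heterogeneity test, multiplicity control, or an exploratory label for subgroup results. The random forest step compares responders with non-responders and does not mention arm, so it does not fill the gap.

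The subgroup section also says that, for participants who share fitness tracker data, those data "will be analyzed in conjunction with survey data separately from those who did not share fitness tracker data".

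**The concern.** Whether a treatment works better in one kind of participant than another is a question about the difference between two treatment effects. Testing the arms separately within each level answers another question: whether each level, alone, shows an effect. Each level holds fewer people than the whole trial, so its test has less power. One level can easily reach significance while the other misses it, even when the true effect is the same in both. A paired test within one arm and one level is further still from the question, because it makes no comparison with placebo.

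Placebo is the smallest arm under the 4:4:2 allocation, and every split divides it again. The results are intended for publications, patents and promotional material, so an unsupported statement about who benefits could travel well beyond the analysis.

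**Working it through.** The plan has no figure to reproduce: it states no alpha, power, effect size or subgroup split. What follows is an illustration.

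**Inputs from the documents**
- Allocation high : low : placebo = 4:4:2 (Details Study Procedures).
- Up to about 1,000 invited (Recruitment). This is an estimate of invitations, not a powered sample size.
- Three primary endpoints (Endpoints).
- Six named subgroup factors.

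**Assumptions**
- Two-sided alpha 0.05.
- Two levels per factor, split 50:50 (30:70 as a variation).
- True effect identical in both levels, set to give 80% or 90% overall power for one arm comparison.

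**1. Power in each half.** Overall, z = 1.960 + z(power). A half-sample divides z by √2, so power per half = Φ(z/√2 − 1.960).
- 80% overall: z = 1.960 + 0.842 = 2.802; 2.802/√2 = 1.981; Φ(0.021) = 0.508.
- 90% overall: z = 1.960 + 1.282 = 3.242; 3.242/√2 = 2.292; Φ(0.332) = 0.630.

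**2. Chance that one level is significant and the other is not**, p₁(1 − p₂) + p₂(1 − p₁):

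| True effect | 50:50 split | 30:70 split |
|---|---|---|
| Same in both, 80% overall power | 2 × 0.508 × 0.492 = 0.50 | 0.335 × 0.350 + 0.650 × 0.665 = 0.55 |
| Same in both, 90% overall power | 2 × 0.630 × 0.370 = 0.47 | 0.427 × 0.226 + 0.774 × 0.573 = 0.54 |
| None | 2 × 0.05 × 0.95 = 0.095 | 0.095 |

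Once overall power is fixed, these values do not depend on the total sample size. An interaction test would be falsely positive 5% of the time in every row.

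**3. Six factors on the same participants.** Results for different factors are correlated, so this was simulated: 2,000 runs, one endpoint, 400 high dose against 200 placebo, six independent 50:50 factors. At least one factor showed a split in significance in 88% of runs at 80% power, 83% at 90% power and 33% with no effect. At least one false interaction arose in 26% to 28% of runs, against 1 − 0.95⁶ = 26.5% by formula.

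**4. Number of tests.** 6 factors × 2 levels × 3 primary endpoints = 36 per arm comparison; 36 × 0.05 = 1.8 false positives expected under no effect. Two comparisons (pooled doses against placebo, and high against low) give 72 and 3.6. All three arm pairs give 108 and 5.4. Expected counts do not require the tests to be independent.

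**5. Placebo numbers.** If 1,000 took part, 200 would receive placebo: 100 per level of a 50:50 factor, or 60 in the smaller level of a 30:70 factor, before the 50% survey-completion rule removes anyone.

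**6. Power of the interaction test.** With a 50:50 split, the standard error of the difference between level effects is twice that of the overall effect. For an interaction as large as the effect detectable at 80% power, power is Φ(2.802/2 − 1.960) = Φ(−0.559) = 0.29. It reaches 80% only for an interaction twice that size.

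**The case against.** The plan has no rule for declaring differential benefit, and nowhere says that significance in one level will be set against non-significance in another. Its language is about understanding, and showing results by level is ordinary practice. A reader might infer that false subgroup claims would be reported; the text supports only that they could be. What stands is that the plan seeks the size of benefit in subpopulations and names no method that can say whether it differs.

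A reader might also infer that benefit is to be compared between tracker sharers and non-sharers. The documents do not say so. Non-sharers have no tracker data, so a split by data availability is the natural reading. Details Study Procedures also has tracker data answering the sleep questions, which is a possible reason for separate handling.

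It would be wrong to describe the 50% as a false-discovery rate. If the effect is real in every level, a significant level is a true finding. The figure measures disagreement in significance, which misleads only when taken as evidence of a difference in effect.

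The highest count, 108 tests, needs two levels per factor and three arm pairs, neither of which is stated. If subgroup work follows only after an overall difference is seen, as Analysis Objectives may imply, the no-effect counts overstate the exposure.

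Finally, the objective of identifying types of benefit in a broad population concerns which benefits appear, not whether they differ between subgroups. The subgroup aim rests on Data Management and Analysis Objectives alone.

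**Conclusion.** The point holds for the named factors and the open-ended remainder. The plan sets a method, separate analysis by level, that cannot answer the question it is meant to serve, and nothing elsewhere supplies one that can. Under the assumptions shown, disagreement in significance between two levels with the same effect is about an even chance for a trial with reasonable overall power, and 9.5% with no effect, against 5% for an interaction test. All percentages depend on the assumed alpha, power and splits; the test counts depend on the number of levels and arm comparisons.

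The consequence is limited to statements about who benefits and by how much. The main arm comparisons are untouched. The change is cheap and should be made before outcomes are examined by arm.

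**What to change.** - List the subgroup factors in full, closing the open-ended category, and fix levels or cut-points before outcomes are examined by arm.
- For each primary endpoint and each listed factor, fit a separate linear model of the change score on arm, factor and arm-by-factor interaction. State which arm comparisons the interaction is reported for.
- Base any statement of differential benefit only on the interaction estimate and its confidence interval. Show per-level effects in a forest plot.
- Label all subgroup results exploratory. This is needed even with interaction tests: six of them, for one endpoint and one arm comparison, still give about a 26% chance of at least one false positive.
- Analyse survey endpoints for the main comparison in sharers and non-sharers together. Keep the tracker-sharer analysis as a description of the tracker data. If benefit in the two groups is to be compared, treat sharing as one more factor.
- Amend Programming Plans if a regression library is wanted, since that section assigns all statistical analysis to NumPy and SciPy.

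The cost is SAP wording and a few lines of code on data already collected. The downside is low power for interactions, so fewer subgroup claims can be made.

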- Have a significant acute or chronic coexisting illness, disorder, or condition that contraindicates, in the Principal Investigator's judgment, entry to the study.
- Currently taking immunosuppressive medications.
- Is considered immunosuppressed for any reason.
- Currently taking medications that could impair the integrity of the gut epithelia
- Has symptoms or an illness, disorder, or cognition that impairs the integrity of the gut epithelia.
- Current antibiotic use or planned oral antibiotic use over the course of the study.
- Investigator believes that the participant may be uncooperative and/or noncompliant and should therefore not participate in the study.

Research equity

This research has no direct exclusions related to gender. There are also no direct exclusions related to race or ethnicity.

Vulnerable Populations

Vulnerable populations are not specifically targeted in this research. Racial and ethnic minorities will be included in the participants but are not specifically targeted for inclusion.

Study Procedures

See Figure 1 for details of study procedures.

Recruitment

Participants will be recruited to the study via email and social media. Interested participants will sign up through the online study landing page. Participants will be chosen from the pool of signups based on the

inclusion and exclusion criteria above. There is no maximum number of participants. All those eligible will be invited to participate. However, we estimate up to 1,000 participants will be invited to participate in the study.

Details Study Procedures

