Once participants are invited to the study, they will be sent an email with a link to the Chloe application, which they will download to their mobile device. Chloe will lead them through a detailed description of the study and the informed consent process. At this point, they will also consent to sharing their fitness tracker data, as an option, if they have one. The fitness tracker data will be used to answer sleep questions and other fitness tracker data will be stored for analysis by the FitBiomics team. Once informed consent is obtained, participants will fill out a baseline health and lifestyle survey, where they will also share their mailing address. Once this survey is completed, the participant will be randomized to a high dose Veillonella (15 billion cfu), low dose Veillonella (7.5 billion cfu), or placebo in a 4:4:2 ratio respectively. These capsules will be mailed to the participant during the 2 week baseline period.

Completion of the initial baseline health and habit survey initiates the 2 week baseline period. During this period, participants will fill out daily surveys on sleep, energy, and bowel movements and weekly surveys on other benefits and adverse events (AEs) they have noticed (more details on all surveys can be found in Tables 1 and 2). On the final day of the two week baseline, they will also fill out the Multidimensional Fatigue Inventory (MFI) and General Self-Efficacy (GSE) questionnaires. At this point, participants will begin supplementation. Participants will supplement with one capsule daily for 4 weeks. During the supplementation phase, participants will fill out the same daily and weekly surveys. On the final day of the supplementation period, participants will also fill out the Multidimensional Fatigue Inventory and General Self-Efficacy questionnaires. After supplementation, there will be a two week washout period to monitor patients and to understand the lasting effect of any benefits they experienced. During the washout period, participants will again fill out the same daily and weekly surveys. On the final day of the washout period, there will be two additional surveys: one with some additional questions on changes observed throughout the study and one of open ended questions on the whole study experience.

Figure 1. Study Procedures

[figure not shown]

Table 1. Survey Details

| Survey Name | Survey Details | Number of Questions | Estimated Time to complete | Number of Times Used | Total survey time |

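### The 50% weekly-survey rule selects the analysis set after randomisation and discards observed Week 6 MFIs, with no all-randomised analysis beside it

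*Combined protocol and SAP*

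**What the plan says.** The Biostatistical Analysis Plan, under Handling of Missing Values, expects gaps: "There will likely be missing values related to incomplete or missing surveys". It answers them with a completer rule, under which participants will "only be included in the analysis if they completed at least 50% of weekly surveys during each time period: baseline, supplementation, and washout", and with a binning rule: "Values will be binned longitudinally such that each participant included in the analysis has a data point associated with each bin". Several values in one bin are averaged. Bin width is not defined.

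On timing, the protocol's detailed study procedures say of the baseline health and lifestyle survey: "Once this survey is completed, the participant will be randomized". The same event starts the clock: "Completion of the initial baseline health and habit survey initiates the 2 week baseline period". The first capsule comes two weeks later.

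On the outcome, Endpoints lists change in MFI as primary, alongside reported physical fatigue and mental/emotional fatigue. Table 2 schedules the MFI at the end of Week 2 and the end of Week 6 only. The procedures text agrees: "On the final day of the supplementation period, participants will also fill out the Multidimensional Fatigue Inventory and General Self-Efficacy questionnaires".

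Analysis Sets / Populations / Subgroups names the three arms, some subgroups and a fitness-tracker split. It defines no all-randomised population. For the rating-scale endpoints, Statistical Procedures says: "Significant differences between groups for these endpoints will be assessed using an independent T test or Mann-Whitney U test".

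**The concern.** Randomisation makes the arms comparable as randomised. It gives no such protection to a subset chosen later by behaviour that treatment may influence. Three things are at stake.

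- **Observed primary outcomes are discarded.** Two washout surveys, due after the last MFI, decide whether that MFI counts.
- **The rule does not secure the outcome either.** A participant can meet it without a Week 6 MFI, and nothing says what happens then.
- **Loss may differ by arm.** Risk/Safety Information lists mild gastrointestinal upset and anxiety as very common on Veillonella and nothing known on placebo. If people who feel worse stop answering, the supplementation and washout conditions could select on response to treatment. No tabulation of exclusions by arm is planned, so a reader could not check.

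The weekly fatigue ratings differ a little. They run to Week 8 and their primary time point is not named, so washout ratings may belong to the endpoint. Even so, failing the washout condition removes all of that participant's ratings from Weeks 1–6.

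**Working it through.** The plan states no response rate, sample size, power or significance level, so there is no figure of its own to reproduce.

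**1. The rule in counts.** Table 1 gives 8 weekly surveys, and the schedule splits them 2 + 4 + 2 = 8. Fifty per cent means at least 1 of 2, 2 of 4 and 1 of 2.

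**2. Two participants, no assumptions needed.**

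| | Baseline | Supplementation | Washout | Week 6 MFI | In the analysis? |
|---|---|---|---|---|---|
| A | 2/2 | 4/4 | 0/2 | observed | no |
| B | 1/2 | 2/4 | 1/2 | missing | yes |

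**3. How many are removed (response rate assumed).** If surveys are answered independently with probability p, the share kept is

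[1 − (1−p)²] × [1 − (1−p)⁴ − 4p(1−p)³] × [1 − (1−p)²].

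At p = 0.8 this is 0.96 × 0.9728 × 0.96 = 0.897, so 10.3% are excluded. Those lost through washout alone are 0.96 × 0.9728 × 0.04 = 3.7%.

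People differ in how reliably they answer, so I also let each person's rate follow a beta distribution with intraclass correlation 0.3 or 0.5. The MFI was taken as answered either at the person's own rate or only together with the Week 6 weekly survey. Ranges over these six cases:

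| Mean weekly response | Observed Week 6 MFIs deleted, whole rule | Of which washout condition alone | Kept participants with no Week 6 MFI |
|---|---|---|---|
| 90% | 2.1–4.8% | 0.9–1.4% | 3.7–10.0% |
| 80% | 7.4–11.1% | 1.8–3.8% | 6.9–20.0% |
| 70% | 11.8–24.1% | 2.6–8.0% | 9.9–30.0% |

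**4. Effect on the false-positive rate (illustration).** Assume no true effect and a two-sided 5% test of one dose against placebo. Assume too that deleted participants are 0.5 SD worse than those retained in the same arm. With deleted fractions f_A and f_P:

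- Bias = (f_A − f_P) × 0.5 SD.
- SE = √[1/(n_A(1−f_A)) + 1/(n_P(1−f_P))].
- Rejection rate = P(|Z + bias/SE| > 1.96).

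Equal fractions give zero bias and 5.0%. With f_A = 10% and f_P = 5%, bias = 0.05 × 0.5 = 0.025 SD in favour of the active arm. Splitting the observed MFIs 4:4:2:

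| Observed MFIs, all arms | n_A / n_P | SE | Bias/SE | Rejection rate |
|---|---|---|---|---|
| 300 | 120 / 60 | 0.1637 | 0.153 | 5.3% |
| 500 | 200 / 100 | 0.1268 | 0.197 | 5.4% |
| 1,000 | 400 / 200 | 0.0897 | 0.279 | 5.9% |

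The last row is a ceiling, because the protocol says "we estimate up to 1,000 participants will be invited to participate in the study". The 10% against 5% contrast is roughly what 80% against 90% weekly response gives when answering is correlated within a person: 11.1% against 4.8% at correlation 0.3, and 8.6% against 4.0% at 0.5, with the MFI at the person's own rate.

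**The case against.** The strongest reply is that the consequences may be slight. The inflation above is nil to small. The protocol describes the expected gastrointestinal symptoms as mild and passing, and reports that in earlier pilots they did not disturb an exercise test. The rule also counts surveys, not capsules: someone who stops the product but keeps answering stays in. All of this stands, and the documents do not show that loss differs by arm. It does not explain why an observed primary outcome should be thrown away, and the plan contains no check that would show whether the loss was harmless.

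Four stronger readings are tempting and should not be drawn.

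- *That no missing-data method exists.* One does: the completer rule with bin means. It can cover a sporadic missed weekly survey. It cannot help the MFI, which has one value before and one after supplementation.
- *That the bin sentence blocks all partial data.* It rules out only an empty bin. If the bins are the three periods, a participant with 1/2, 2/4 and 1/2 surveys is analysed from partial data.
- *That all three conditions select on treatment response.* The baseline weeks precede the first capsule, so taking the product cannot drive baseline completion. That condition mainly costs data and precision. The whole-rule percentages include baseline failures.
- *That safety data are excluded.* The rule speaks of the analysis without a safety exception, and Data Management plans a safety comparison. But adverse events also reach the study by phone and email, and the plan does not say whether safety comparisons use the rule. This is an ambiguity and adds nothing to the seriousness of the point.

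**Conclusion.** The concern holds on the text. The only overall analysis stated is confined to a set selected after randomisation. The washout condition deletes Week 6 MFIs already on file. No all-randomised analysis, imputation, model-based method or missing-data sensitivity analysis stands beside it.

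Its numerical size cannot be derived from the documents. Under an assumed 70–90% weekly response, about 2–24% of observed Week 6 MFIs would be deleted, about 1–8% through washout alone. A reader might infer that the trial's result will be materially biased. The documents do not support that: bias in the difference is zero if loss is equal across arms and equally related to outcome, and the unequal case illustrated gives 5.3–5.9% in place of 5.0%. Larger inflation needs more extreme loss, on which the documents are silent. The case for change rests on the missing all-randomised analysis and the discarded outcomes, not on these percentages.

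**What to change.** 1. Make the primary between-group comparison all randomised participants with observed data, by assigned arm, so that every observed Week 6 MFI is used whatever the weekly-survey completion. At minimum, remove the washout condition for endpoints measured by Week 6. Add this population to Analysis Sets.
2. Amend the bin sentence so that an empty washout bin does not remove earlier data, and define the bins.
3. Keep the 50% set as a supportive analysis. Observed-data analysis still depends on who answered, so add one missing-data sensitivity analysis: for example, multiple imputation with a delta adjustment, or a mixed model for the weekly ratings. Report exclusions by arm and period.
4. State that the 50% rule does not apply to safety summaries.

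A complete replacement of the planned t and Mann-Whitney tests by modelling is partly a matter of preference and is not needed to cure this defect.

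The cost is SAP wording, some analysis code and probably one more statistics library, since Programming Plans names only Numpy and Scipy for statistical work. No new data or participants are needed.
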